The proposed pilot study described below represents a marked advance on previously-reported trials in that (a) study design is directed towards minimization of systemic bias, and (b) we will perform simultaneous comparisons of multivariate inflammatory and coagulation profile changes over the immediate post-operative time period when inflammatory changes are expected to be at a maximum. The novelty of our approach is our systems-level analysis of lipids and their interacting moieties; new technology in our labs allows for rapid quantitative analysis of over 150 lipid mediators in a sample, time and cost

November 16, 2016

effective manner.

METHODS/DESIGN

LITERATURE SEARCH

A rapid systematic evidence assessment was conducted on three occasions in PUBMED. Search terms, filtered by identifier *clinical trials*, were:

((high dose vitamin C) OR (ascorbic acid)) AND surgery;
((vitamin C) OR (ascorbic acid)) AND (cardiac AND surgery);
(ascorbate OR vitamin C OR ascorbic acid) AND Superoxide AND (Nitric Oxide);

From a total of 285 studies, 20 were retained; the remainder was excluded for lack of relevance or duplication. Studies were archived and analyzed in Review Manager 5.2.¹³

A search of *ClinicalTrials.gov* using the search terms (*ascorbate OR vitamin C OR ascorbic acid*) AND (*cardiac surgery OR cardiovascular*) AND/OR (*IV OR intravenous*) resulted in 9 relevant trials (total 90). As of December 17, 2014, five were completed, one terminated, two of unknown status, and one not yet recruiting; no data from these studies were available.

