- a) Levels of circulating pro-inflammatory biomarkers profiles (CRP, IL-6, TNF- α), NGAL (in urine), and lipid pro- and anti-inflammatory mediators (in plasma);
- b) Levels of coagulation biomarker and platelet function (e.g. fibrinogen, platelet counts, thrombomodulin, R, K, MA, G, angle, LYO)

Specific Aim 2: We will test the prediction that reduced post-surgical inflammatory burden of patients administered high-dose vitamin C will result in clinically significant reductions in hospital-based outcomes (such as length of hospital stay, length of ICU stay.)

STUDY DESIGN

This is a prospective, double-blind, placebo-controlled, randomized pilot trial comparing high-dose intravenous vitamin C to placebo (normal saline) infusions in elective non-emergent cardiac bypass patients. Double blinding will be used at enrollment, randomization, and throughout treatment, sampling, analysis, and data interpretation phases.

The purpose of this pilot study is to demonstrate **performance feasibility** and **proof of concept (PoC)** before initiation of a full-fledged clinical trial. Both financial and personnel constraints limit the total patient enrollment to 24 (12 per arm). Because sample sizes are so small, hypothesis testing cannot be a central feature of this proposal. Instead, success criteria will consist of tangible and measurable performance metrics relating to trial performance and PoC. *Performance success criteria* relate to the logistics and processes involved in the execution of the study itself (e.g. recruitment, retention, study flow, operations, management, obtaining samples, sample processing, documentation, compliance oversight). *Proof of concept* will be determined by large effect size differences (20%) between test and experimental intervention groups in one or more of the key inflammation and coagulation markers (see **OUTCOMES**).

It is unethical to consider running a phase III trial without sufficient data or feasibility information. This pilot trial will be extremely useful to inform the planning and execution of the future large-scale trial, especially with respect to feasibility and sample size calculations. Proof of concept information will be essential for writing major grants, which usually require such preliminary information for assessing scientific validity²¹⁻²³

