Exclusion criteria are: (1) known allergy to Vitamin C; (2) pregnant or breastfeeding; (3) prisoner; (4) emergent cardiac surgery patients; (5) scheduled for single CABG procedure; (6) low ejection fraction ($< 35\%$); (7) current autoimmune disease or on immunosuppressant therapy, including prednisone, prednisolone, dexamethasone, mycophenolate, tacrolimus, cyclosporine, or azathioprine; (8) presence of renal calculi, or renal dysfunction (pre-operative creatinine clearance < 40 , or serum creatinine greater than 1.8 mg/dl); (9) known bleeding diathesis such as hemophilia, Von Willebrand's disease, or liver failure, or receiving concurrent anticoagulant therapy (such as warfarin, dabigatran or apixaban) for venous or arterial thrombosis; (10) active infection or tumor; (11) prior history of atrial fibrillation (AF); (12) known diagnosis of diabetes mellitus, or preoperative (this surgery) A1C test result ≥ 6.5 ; (13) diagnosed with diabetic ketoacidosis

November 16, 2016

(DKA); (14) known coagulopathy prior to surgery (INR > 1.5).

Patient numbers/sample size: This is a feasibility/ proof of concept pilot trial; therefore power calculations are not appropriate. Patient enrollment numbers are limited *a priori* by the funding available for this project and costs inherent to enrollment, randomization and blinding procedures, sampling, and sample processing.

Consent Procedures. All eligible patients will be approached prior to their scheduled surgery by the study coordinator or attending surgeon. A formal Institutional Review Board (IRB)-approved Informed Consent form will be discussed with the patient, and all questions answered prior to obtaining informed patient consent in writing. Informed consent will be documented in the patient medical record, and the clinical research office and each enrolled patient will receive a copy of his/her signed consent form.

INTERVENTION AND CONTROLS

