This is a two-arm trial comparing high-dose IV vitamin C to normal saline placebo controls (Fig. 1). Once informed consent is obtained, the time of surgery will be communicated to the VCU investigational pharmacy so that the medication can be appropriately prepared and delivered to the operating room. Prior to preparation, patients will be randomized to receive either control or Vitamin C solution. Randomization will be performed by a computer-generated permuted block design conducted by the investigational pharmacy. Both test and placebo preparations will be prepared by pharmaceutical staff in identical de-identified 50-mL medication bags so as to be indistinguishable by OR/ICU staff and investigators.

Vitamin C will be administered in doses of 200 mg/kg/day group divided into four doses per day at six hour intervals 48 hours. Patients randomized to the control (normal saline) group will receive equivalent fluid volume in identical dispensing bags; total study fluid volumes will be approximately 400 mL over the two-day study period. Blinded interventions will be administered in the OR by the anesthesiologist, and post-operatively by Cardiac Surgery ICU nursing staff and/or Cardiac Stepdown Units. All participating hospital units will be provided with thorough in-servicing. Nurses will be prompted to administer the medication via the patient-specific electronic medical record (EMR).

OUTCOMES

Enrollment Goals: (1) Up to 40 may be enrolled in order to reach completion of 24 out of 24 subjects to allow for withdrawals; (2) complete follow-up and follow-up data for 24/24 (100%) of enrolled subjects; (3) all patients (24/24) to receive study drug according to randomization designation; (4) all patients (24/24) to receive every scheduled dose of the study drug in a blinded manner; (5) all patients (24/24) to have coagulation and biolipid determinations performed for all.

Biomarker outcomes:

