Patients will not be paid for participation and there will be no penalties imposed for either refusal to participate or withdrawal of consent after enrollment.

Patient Drop-Out. Patients may refuse consent and leave the study at any time for any reason. This will be done by notifying the study physician or study coordinator. Subjects can be withdrawn from the study emergently by the attending study physician if they

November 16, 2016

develop signs and symptoms of adverse reactions.

DATA ANALYSES

Baseline demographic and clinical characteristics of study participants will be reported as descriptive summary statistics. Categorical variables will be reported as absolute and percent values. Continuous variables will be expressed as means and standard deviations, or median and interquartile ranges.

For each primary and secondary outcome, we will report the point estimate of effect and its precision (e.g. 95% confidence interval).

Biomarkers will be analyzed both individually and as clusters, or constellations, of variables. These clusters will be determined by exploratory factor analysis, discriminant analysis and/or vector analysis. Each cluster can be interpreted as a specific pathophysiological network process. The clusters can then be used as an empirical model to determine inter-dependencies between individual biomarkers. Discriminant function analysis is used to predict patient membership in either the Vitamin C treatment group or the control group by the entire suite of inflammation and coagulation variables (the predictor variables). Unlike cluster analysis, discriminant analysis is used when groups are known *a priori*. The measures of effect size are the *canonical correlation* (correlation between groups and the function), the *proportion of variance for each function*, calculated as $(\lambda_x/\Sigma\lambda_i)$ where λ_x is the eigenvalue for the function and $\Sigma\lambda_i$ is the sum of all eigenvalues, and *percent correctly classified*.³⁴ Finally vector analysis³⁵ can allow determination of the simultaneous directional change of all the measured inflammatory, biolipid and/or coagulation markers as a function of treatment group. These techniques allow a comparison of dynamic responses rather than a direct comparison of static levels which may not be particularly revealing of complex patterns of interactions between multiple variables.

No interim analyses will be performed because this trial is a small pilot.

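### With 24 patients and no rule for keeping factors, the plan cannot tell chance biomarker clusters from weak or moderate real ones, yet it allows each to be read as a disease process

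*Combined protocol and SAP*

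**What the plan says.** The DATA ANALYSES section says that biomarkers will be analysed singly and in groups. On the groups it says: "These clusters will be determined by exploratory factor analysis, discriminant analysis and/or vector analysis". It continues "Each cluster can be interpreted as a specific pathophysiological network process", and then "The clusters can then be used as an empirical model to determine inter-dependencies between individual biomarkers".

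The STUDY DESIGN section sets the size at 24 patients, 12 per arm. The sample-size paragraph gives funding as the reason and adds: "This is a feasibility/ proof of concept pilot trial; therefore power calculations are not appropriate".

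The plan does not give the list or number of markers entering the factor analysis, the extraction method, the retention rule, the rotation, a loading cut-off or any resampling check. It also does not say how the four blood draws per patient, or the two arms, enter the analysis. The small-sample paragraph under LIMITATIONS OF PROPOSED RESEARCH concerns statistical significance and differences between groups. It does not mention the stability of factors.

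**The concern.** Factor analysis always returns factors. Whether they mean anything depends on the number of patients, the number of markers and the strength of the real correlations. With 24 patients the sample correlations are very imprecise: two unrelated markers must exceed |r| = 0.404 to reach two-sided 5% significance. Chance correlations of that order are numerous enough to be gathered into factors that look orderly.

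The plan attaches its mechanistic reading to every cluster and gives no condition under which the reading would be withheld. It then treats the clusters as a model of how markers depend on one another. Followed as written, it would allow a chance grouping to be reported as a biological network, and a reader of the report could not detect this from the usual summaries.

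**Working it through.** The plan gives no figure for this analysis, so there is nothing to reproduce. The check asks what the planned analysis would show if there were no structure at all.

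**Inputs from the document**
- Patients: 24 (STUDY DESIGN).
- Named non-lipid markers: 9 coagulation items in Specific Aim 1 (fibrinogen, platelets, thrombomodulin and six viscoelastic readings), plus CRP, IL-6, TNF-alpha, NGAL, white cells and creatinine (Specific Aim 1 and OUTCOMES). That is 9 + 6 = 15.
- Lipids: a targeted subset, number not stated (OUTCOMES, Lipidomics).
- Blood draws: four per patient (POST-RANDOMIZATION TREATMENT), so at most 4 × 24 = 96 rows, which are not independent.

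**Assumptions, because the plan is silent**
- Normal data and principal-component extraction with varimax rotation.
- Factors kept if the eigenvalue exceeds 1, and a loading counted as high at 0.6 or more.
- Comparison data have three real factors, each marker loading *l* on one of them: x = *l*·f + √(1 − *l*²)·e. Two markers on the same factor then correlate at *l*², which is 0.25 at *l* = 0.5 and 0.49 at *l* = 0.7.

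**Formulas.** The eigenvalues of a p × p correlation matrix sum to p. Variance explained is the sum of the eigenvalues above 1, divided by p.

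**Simulated means, one row per patient, n = 24**

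| Data | Markers | Factors kept | Variance explained | Markers with a high loading |
|---|---|---|---|---|
| Noise | 15 | 6.4 | 75% | 78% |
| Three factors, loading 0.5 | 15 | 5.8 | 76% | 81% |
| Three factors, loading 0.7 | 15 | 4.2 | 74% | 93% |
| Three factors, loading 0.85 | 15 | 3.0 | 79% | 99% |
| Noise | 30 | 11.4 | 85% | 70% |
| Three factors, loading 0.5 | 30 | 10.1 | 83% | 72% |
| Three factors, loading 0.7 | 30 | 7.6 | 82% | 89% |

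For noise on 15 markers, the retained eigenvalues sum to about 0.75 × 15 = 11.25, or 11.25 / 6.4 ≈ 1.76 each, although every population eigenvalue is 1.

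**Does it replicate?** The congruence of three-factor solutions from two independent samples of 24, on 15 markers, is 0.32 for noise, 0.51 at loadings of 0.5, 0.87 at 0.7 and about 0.95 at 0.85.

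**Would the repeated draws rescue it?** Treating all 96 rows as independent is the most favourable case and is not justified. Noise on 30 markers still gives 13.4 factors explaining 68%.

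**Would a threshold help?** If a factor is kept only when its eigenvalue exceeds the 95th percentile from structureless data, noise yields a factor in about 5% of runs. At loadings of 0.7, all three real factors are found in roughly 60 to 70% of runs with 15 markers and about 90% with 30. At loadings of 0.5 with 15 markers, all three are found in only a few per cent of runs.

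**The case against.** The strongest defence is that this is an exploratory pilot. The wording is permissive, factor analysis is one of three techniques joined by and/or, markers are also analysed individually, and hypothesis testing is expressly not central. All of that is true, and it limits how much rides on the point. It does not answer it: the label describes the method, while the interpretive sentence covers every cluster and sets no criterion.

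A second defence is that independent noise is a null, not a forecast. Several coagulation readings appear to come from one viscoelastic test, and the lipids centre on one metabolic pathway, so real correlation is likely. This stands. But correlation that arises because readings share an assay, or because all markers follow the same time course after surgery, would also form stable clusters without each being a distinct process.

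Four stronger readings are tempting, and the documents do not support them:
- *Noise gives factors as clear as any real ones.* Not so. At 30 markers and loadings of 0.7, the first eigenvalue is 7.9 against 3.9 for noise, and two-sample congruence is 0.88 against 0.21.
- *The analysis involves more than 150 markers and so cannot be fitted.* The introduction's statement that "new technology in our labs allows for rapid quantitative analysis of over 150 lipid mediators in a sample" describes what the assay can do. The Lipidomics paragraph speaks of a subset, and the limitations section says few markers will be screened. The plan does not name a fitting method that would fail.
- *The clusters decide the next trial.* Proof of concept is defined by a 20% difference in key markers, and the options under FUTURE RESEARCH do not mention clusters.
- *A short marker list or a single draw would solve it.* Noise on 10 markers still gives 4.4 factors explaining 71%. With 9 markers, the chance of finding all three real factors at loadings of 0.7 falls to about 27%. A single draw would also defeat the stated aim of comparing dynamic responses.

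**Conclusion.** The concern holds in a limited form. With 24 patients and no retention or stability rule, chance factors cannot be told from weak or moderate real ones, so the reading given to each cluster is unsupported. On the 15 named non-lipid markers the usual summaries barely differ: 6.4 factors and 75% for noise, against 5.8 factors and 76% for real loadings of 0.5. The conclusion does not depend on how many lipids are added. Structure with loadings of about 0.7 or more is recoverable at this sample size, provided the plan adopts a rule that looks for it.

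The exact figures rest on the eigenvalue-above-1 rule, normal data, simple structure and principal-component extraction, none of which the plan specifies. Other choices would change the numbers. The feasibility goals and the individual-marker analyses are unaffected. This is a correction that should be made, not one that threatens the trial.

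**What to change.** Amend the DATA ANALYSES section as follows:
- List in advance the markers that enter the factor analysis.
- State how the four blood draws and two arms are handled, for example by within-arm residuals or change scores, with the patient as the resampling unit. Urine has its own schedule (baseline, 6 and 24 hours), so say how NGAL is aligned with the blood markers.
- Keep only factors whose eigenvalues exceed the 95th percentile obtained by permuting each marker across patients.
- Report the stability of loadings from a bootstrap that resamples patients.
- Replace the interpretive sentence with: *clusters are hypothesis-generating and will not be interpreted as pathophysiological processes unless replicated*.

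No extra patients, samples or assays are needed. The cost is a little programming and fewer reported clusters. Some real but weak clusters will be missed, which is unavoidable with 24 patients and should be stated.

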With very few exceptions, most studies were characterized by high risk of bias in six bias domains (selection, performance, detection, attrition, reporting, other).¹⁴ Lack of randomization and blinding, and failure to explicitly define clinical outcomes contributed to these problems. The majority of studies used oral vitamin C supplementation. Oral doses, even those in excess of 200 mg, are associated with little or no clinically significant increases in circulating Vitamin C levels¹⁵, and pharmacokinetics of oral ascorbic acid dosing differs considerably from intravenous dosing.¹⁶ However most assessed studies reported positive effects of vitamin C supplementation. Meta-analysis of these papers indicated a significant overall reduction in both post-operative AF (9 studies; n= 1039 patients; odds ratio 0.37 [95% CI 0.28, 0.50]) and a small reduction in length of hospital stay (6 studies; n= 672 patients; mean difference -1.3 days [95% CI -1.6, -1.0]). A few papers reported measurements of isolated inflammatory and coagulation markers; however, results were equivocal. For example, vitamin C supplementation of CABG patients (usually in combination with various antioxidant cocktails) seemed to attenuate post-operative oxidative stress,¹⁷ myocardial “injury” (defined as a five-fold elevation of cardiac biomarker values and cardiac dysrhythmia),¹⁸ and endothelial dysfunction.¹⁹ In contrast, a study of cardiac surgery patients on or off CPB did not detect statistically significant differences between oral vitamin C and control groups in C-reactive protein (CRP) concentration, white blood cell (WBC) count, or fibrinogen concentration, markers of inflammation and coagulopathy.²⁰ However the study was underpowered because of early study termination, and data were uncorrected for non-normality, invalidating subsequent statistical analyses. In summary, although suggestive of benefit, current evidence of efficacy of high-dose vitamin C was of low quality with limited and/or irrelevant outcomes, necessitating development of more rigorous clinical trials.

SPECIFIC AIMS

Specific Aim 1: We will test the prediction that patients administered high-dose vitamin C will show clinically-significant reductions in pro-inflammatory and coagulation markers at peak response and at 48 hours relative to normal saline controls. Specifically, we will measure

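### The 24-patient discriminant analysis has no stated validation or chance reference: one of its three effect sizes is always 100%, and the other two run high under no effect if computed on the fitted patients

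*Combined protocol and SAP*

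**What the plan says.** The Data Analyses section will study biomarkers singly and in clusters, using factor analysis, discriminant analysis and/or vector analysis. The discriminant analysis is to "predict patient membership in either the Vitamin C treatment group or the control group by the entire suite of inflammation and coagulation variables". Its effect sizes are the canonical correlation, the "proportion of variance for each function" (the function's eigenvalue divided by the sum of all eigenvalues), and "percent correctly classified".

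The section does not say which markers enter, at which time, or whether classification is scored on the fitted patients or on left-out patients. It gives no chance rate. It says the techniques permit a "comparison of dynamic responses rather than a direct comparison of static levels", which may mean change scores.

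The possible predictors appear elsewhere:

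- Specific Aim 1 names CRP, IL-6, TNF-alpha and urinary NGAL, and, as examples, the coagulation measures "fibrinogen, platelet counts, thrombomodulin, R, K, MA, G, angle, LYO". It sets the comparison "at peak response and at 48 hours relative to normal saline controls".
- The same aim lists "lipid pro- and anti-inflammatory mediators (in plasma") beside the inflammatory markers.
- The Outcomes section adds white cell count, and says that creatinine will be followed.
- Study Design fixes 24 patients, 12 per arm. It defines proof of concept separately, as a 20% difference in one or more key markers.

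**The concern.** Discriminant analysis picks the weighted sum of markers that best separates the two arms in the data at hand. When the number of markers is more than half the number of patients, that sum separates the arms well by chance alone. Accuracy and canonical correlation computed on the same patients then look strong for a treatment that does nothing.

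The pilot is meant to supply preliminary evidence for a main trial and for grant applications. If it reported 88% correctly classified without a chance reference, readers would probably take that as a clear multivariate response. The Limitations section asks readers not to emphasise significance and notes low power. That guards against over-reading p-values and says nothing about overfitting. It also shifts attention to effect sizes, which are the quantities affected here.

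**Working it through.** The plan states no expected classification rate, so there is no figure of its own to reproduce.

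**Inputs.** N = 24, with 12 per arm (Study Design). Specific Aim 1 names 4 inflammation and 9 coagulation markers: 4 + 9 = 13. White cell count makes 14, and creatinine, if counted, 15. Urine is collected at baseline, 6 h and 24 h only, so at 48 h NGAL drops out: 13 − 1 = 12 markers, or 13 with white cell count. The lists are open, so every count is an assumption. Using change scores leaves the count per time point the same.

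**1. Proportion of variance.** The number of functions is min(groups − 1, predictors) = min(1, p) = 1. With one non-zero eigenvalue, λ₁/Σλ = λ₁/λ₁ = 1 for any data. In a simulated data set with 14 predictors the first eigenvalue was 1.16, the rest were at rounding error, and the ratio was 1.

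**2. Canonical correlation under no effect.** For normal markers, r² follows Beta(p/2, (23 − p)/2). Mean r² is p/23: 13/23 = 0.565 and 14/23 = 0.609. The exact mean of r is 0.746 for 13 markers and 0.775 for 14. So the chance reference is not zero.

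**3. Percent correct under no effect, scored on the fitted patients.** Ordinary linear discriminant, equal priors, independent normal markers, at least 10,000 simulated trials per row:

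| Predictors | Mean % correct | Null trials with at least 80% correct | Mean canonical correlation |
|---|---|---|---|
| 4 | 67% | 4% | 0.40 |
| 8 | 76% | 27% | 0.58 |
| 9 | 78% | 37% | 0.62 |
| 12 | 85% | 67% | 0.72 |
| 13 | 87% | 76% | 0.75 |
| 14 | 89% | 84% | 0.77 |
| 15 | 91% | 90% | 0.80 |

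The averages barely move with other marker distributions. With correlation 0.5 between markers they are 86.8% (13 markers) and 89.1% (14). With log-normal markers they are 86.1% and 88.2%.

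**4. Leave-one-out scoring under no effect.** The mean is 49.4% correct for 13 markers and 48.9% for 14. A single null trial ranges from about 29% to 71% (5th to 95th percentile).

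**5. Limit on predictors.** The pooled within-arm covariance has 24 − 2 = 22 degrees of freedom. With more than 22 predictors it is singular, and the ordinary discriminant function cannot be computed.

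**The case against.** The strongest case on the other side is that nothing hangs on this analysis. It is exploratory and one of several and/or options, so it may not be run. No threshold is attached to it, and proof of concept rests on the 20% rule. Markers are also analysed individually, and each primary and secondary outcome gets a point estimate and precision. All of this stands. It limits the consequence to interpretation, but it does not make the named measures informative.

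Three stronger readings are tempting and are not supported.

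- **That the plan scores accuracy on the fitted patients.** It is silent. The 87% is what follows if it does so with 13 markers. With 8 or 9 markers the figure is 76–78%.
- **That the analysis cannot be computed because lipids are included.** The introduction mentions "rapid quantitative analysis of over 150 lipid mediators", but that describes laboratory capability, and the lipidomics plan is for a targeted subset. Specific Aim 1 groups lipids with the inflammatory markers, whereas Outcomes and the vector-analysis sentence in Data Analyses treat them as a separate class. Singularity arises only if lipids enter and the predictors exceed 22.
- **That even perfect apparent classification could never stand out from chance at 13 or more predictors.** With normal markers, 100% correct occurs in about 7% of null trials at 13 predictors and 11–12% at 14. With log-normal markers at 13, it occurs in only about 4% of label permutations on average, and in about 85% of data sets it falls at or below 5%. No general statement of that kind holds.

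It is also fair to say that leave-one-out accuracy is imprecise with 24 patients. Under an assumed 0.8 SD shift, with correlation 0.3 between markers, the 14-marker suite averages only 59–61%. A 5% pass mark would also sit badly in a pilot that says hypothesis testing is not central to it.

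**Conclusion.** The point holds as a gap in specification and reporting. The proportion of variance is 100% by algebra, whatever the data, and carries no information. The other two measures cannot be interpreted until the predictors, time point and scoring method are stated. If they are computed on the fitted patients, an inert treatment averages about 87% correct and a canonical correlation of 0.75 with 13 markers, and about 89% and 0.775 with 14. Leave-one-out accuracy is then about 49%.

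These figures assume 12 per arm with complete data, a single time point, an ordinary linear discriminant and same-patient scoring. Correlated or skewed markers leave the averages almost unchanged.

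A reader might infer that the pilot's success criterion is compromised. It is not, because the 20% rule is separate. The effect is on how much weight the multivariate result deserves in planning the larger trial. The change should be made before the data are analysed.

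**What to change.** In the Data Analyses section:

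- Delete the proportion-of-variance measure.
- Fix the predictor set and the time point in advance, without using arm labels, and say whether lipids and change scores are included.
- Report leave-one-out accuracy beside any apparent accuracy, with any data reduction repeated inside each fold.
- State the numbers of predictors and patients with every accuracy and canonical correlation.
- Give the label-permutation distribution of leave-one-out accuracy and of the canonical correlation as a descriptive chance reference, not as a 5% pass/fail rule.

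Scores from the factor analysis already planned, or a penalised discriminant, are options and not requirements. Factor scores are harder to read than single markers. Whether they improve accuracy depends on how many markers respond.

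The cost is some wording and a few lines of code, with no new data. The downside is slightly more analysis work and less impressive-looking figures.
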